3 OBJECTIVES

3.1 Primary Objective

The primary objective is to assess the safety and tolerability of BMS-986183 administered as monotherapy and in combination with nivolumab in subjects with HCC.

3.2 Secondary Objective

- To assess the preliminary anti-tumor activity of BMS-986183 administered as monotherapy and in combination with nivolumab as measured by objective response rate (ORR), response duration, and progression-free survival (PFS)
- To characterize the PK of the total antibody (unconjugated antibody + antibody conjugated to tubulysin or antibody conjugated to any tubulysin metabolites), active antibody drug conjugate (ADC; antibody conjugated to tubulysin), and unconjugated tubulysin of BMS-986183 as monotherapy and in combination with nivolumab
- To assess the effect of dosage regimen and exposure (active ADC and unconjugated tubulysin) of BMS-986183 as monotherapy on the QT interval
- To characterize the immunogenicity of BMS-986183 as monotherapy and in combination with nivolumab

4 ENDPOINTS

4.1 Primary Endpoints

Primary endpoints will include incidence of AEs at their worst grade, SAEs at their worst grade, AEs leading to discontinuations, deaths, and frequency of laboratory test toxicity grade shifting from baseline. Safety will be evaluated from the time that the subject signs the informed consent and for up to 60 days after the last dose of study drug for BMS-986183 monotherapy dose

escalation period (Part 1) and BMS-986183 monotherapy dose expansion period (Part 2) and up to 100 days after the last dose of study drug for BMS-986183 and nivolumab combination therapy dose escalation (Part 3) and BMS-986183 and nivolumab combination therapy dose expansion (Part 4). AEs and laboratory values will be graded according to the National Cancer Institute (NCI) Common Terminology Criteria for Adverse Events (CTCAE) version 4.03.

4.2 Secondary Endpoints

4.2.1 Efficacy Endpoints

Efficacy endpoints that are based on tumor response data will be derived per RECIST v1.1 response criteria.

- **Best overall response (BOR)**, defined as the best response designation over the study as a whole, and recorded between the date of first dose until the last tumor assessment prior to subsequent anticancer therapy and the date of first objectively documented progression per RECIST v1.1, whichever occurs first. CR or PR determinations included in the BOR assessment must be confirmed by a second scan performed no less than 4 weeks after the criteria for response are first met. For those subjects who have surgical resection, only pre-surgical tumor assessments will be considered in the determination of BOR.
- **Objective Response Rate (ORR)**, defined as the total number of subjects whose BOR is either a CR or PR divided by the total number of subjects in the population of interest.
- **Duration of Response (DOR)**, defined as the time between the date of first response and the subsequent date of objectively documented disease progression or death, whichever occurs first. For those subjects who remain alive and have not progressed or received subsequent anticancer therapy, duration of response will be censored on the date of last tumor assessment. For subjects who received subsequent anticancer therapy, duration of response will be censored on the date of last tumor assessment prior to initiation of subsequent anticancer therapy. Response duration will only be evaluated in participants with a BOR of CR or PR.
- **Progression Free Survival (PFS)**, PFS for a subject is defined as the time from the first dose of study drug to the date of first objectively documented disease progression per RECIST v1.1 or death due to any cause, whichever occurs first. Clinical deterioration in the absence of radiographic evidence is not considered progression for the purpose of determining PFS. Participants who died without a reported prior progression will be considered to have progressed on the date of their death. Participants who remained alive and have not progressed will be censored on the last tumor assessment date. Participants who started subsequent anticancer therapy (defined as anticancer therapy initiated after the start of study treatment) without a prior reported progression will be censored at the last tumor assessment prior to initiation of the subsequent anticancer therapy. Participants who did not have any post-baseline tumor assessment and did not die will be censored the date of randomization. Censoring algorithm for PFS is listed in **Error! Reference source not found.**
- **PFS rate at week 't'**: defined as the proportion of subjects who remain progression free and surviving at 't' weeks (t=12, 24, 36, etc). The proportion will be calculated by the product-limit method (Kaplan-Meier [K-M] estimate) which takes into account censored data.

Table 4.2.1- 1: Censoring Scheme for analysis of PFS

Situation	Date of Progression or Censoring	Outcome
No baseline tumor assessments	Treatment start date	Censored
No on study tumor assessments and no death ^a	Treatment start date	Censored
Subsequent anticancer therapy ^b started without a prior reported progression per RECIST v1.1 criteria	Date of last tumor assessment prior or on the date of initiation of the subsequent anticancer therapy ^b	Censored
No progression or clinical progression without evidence of progression per RECIST v1.1 criteria	Date of last tumor assessment ^a with no documented progression	Censored
Progression per RECIST v1.1 criteria documented between scheduled visits or at scheduled visit without prior subsequent anticancer therapy ^b started	Date of the first documented tumor progression per the RECIST v1.1 criteria	Progressed
Death without progression per RECIST v1.1 criteria and without prior subsequent anticancer therapy ^b started	Date of death	Progressed

^a Tumor assessments and death if any, occurring after start of subsequent anticancer therapy are not considered.

^b Subsequent anticancer therapy is defined as the following therapy which started after the treatment start date: systemic anti-cancer/anti-neoplastic therapy, any investigational drug or palliative local therapy.

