All subjects will enter the safety follow-up period once the decision is made to discontinue the subject from treatment (eg, at end of treatment [EOT]).

After the EOT visit, all subjects will be evaluated for any new AEs for a total of 60 days after the last dose of study drug for BMS-986183 dose escalation (Part 1) and BMS-986183 dose expansion (Part 2) and for a total of 100 days after the last dose of study drug for BMS-986183 and nivolumab dose escalation (Part 3) and BMS-986183 and nivolumab dose expansion (Part 4). Follow-up visits should occur at 30 and 60 days (\pm 5 days) after the last dose. Subjects in BMS-986183 and nivolumab dose escalation (Part 3) and BMS-986183 and nivolumab dose expansion (Part 4) will have an additional visit at 100 days (\pm 10 days) after the last dose. All subjects will be required to complete their clinical safety follow-up visits regardless of whether they start new anti-cancer therapy, except those subjects who withdraw consent for study participation.

Subjects who develop toxicity requiring discontinuation of treatment will enter the safety follow-up period. The subject should be seen at least every 30 days, until the AE has resolved to baseline, stabilized, or been deemed irreversible.

Survival Follow-up Period

After completion of the safety follow-up period, all subjects will enter the survival follow-up period. All subjects will be followed by telephone contact, office visit, or documented clinic visit every 12 weeks (\pm 2 weeks) from his/her last dose of study drug for 6 months until progression or death. Both response and survival follow-up periods will occur simultaneously during the 6-month follow-up period. The duration of this period is up to 6 months following the subject's last dose of study drug. Subjects in the survival follow-up period who progress will be eligible to receive anti-cancer therapy as appropriate.

Retreatment during Survival Follow-up (Parts 3 and 4 only)

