8.3.2 Secondary Endpoint(s)

The first secondary objective (to assess the preliminary anti-tumor activity of BMS-986183 administered as monotherapy and in combination with nivolumab as measured by ORR, response duration, and PFS) will be measured by the following secondary endpoints:

- Best overall response (BOR): defined as the best response designation over the study as a whole, recorded between the dates of first dose until the last tumor assessment prior to subsequent therapy. CR or PR determinations included in the BOR assessment must be confirmed by a second scan performed no less than 4 weeks after the criteria for response are first met. For those subjects who have surgical resection, only presurgical tumor assessments will be considered in the determination of BOR.
- ORR: defined as the total number of subjects whose BOR is either a CR or PR divided by the total number of subjects in the population of interest.
- Duration of response (DoR): defined as the time between the date of first response and the subsequent date of objectively documented disease progression or death, whichever occurs first. For those subjects who remain alive and have not progressed or received subsequent therapy, DoR will be censored on the date of last tumor assessment
- PFS: defined as the time from the first dose of study drug to the date of the first objective documentation of tumor progression or death due to any cause. Subjects who did not progress nor died will be censored on the date of their last tumor assessment. Subjects who did not have any on-study tumor assessments will be censored on the date of the first dose of study drug. Subjects who started any subsequent anti-cancer therapy without a prior reported progression will be censored at the last tumor assessment prior to initiation of the subsequent anti-cancer therapy. Subsequent anti-cancer therapy will be defined as the following therapy, which started after the treatment start date: systemic anti-cancer/anti-neoplastic therapy, any investigational drug, or palliative local therapy.
- PFS rate at week 't': defined as the proportion of subjects who remain progression free and surviving at 't' weeks (t=12, 24, 36, etc). The proportion will be calculated by the product-limit method (Kaplan-Meier [K-M] estimate) which takes into account censored data.

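### The SAP's duration-of-response bullet contradicts itself: progression is the event, yet responders who progress and then start new therapy are censored, which would lengthen the Kaplan-Meier DOR if programmed as written

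*SAP*

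**What the plan says.** The DOR bullet in SAP 4.2.1 has three relevant parts.

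- **Event.** The endpoint is "defined as the time between the date of first response and the subsequent date of objectively documented disease progression or death, whichever occurs first".
- **Ordinary censoring.** Living responders with neither progression nor later anticancer treatment are censored at their most recent scan.
- **Censoring for later therapy.** "For subjects who received subsequent anticancer therapy, duration of response will be censored on the date of last tumor assessment prior to initiation"; what is initiated here is the later treatment.

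The next bullet, for PFS, handles the same situation with a condition. Under it, people who begin a new treatment "without a prior reported progression will be censored at the last tumor assessment prior to initiation of the subsequent anticancer therapy". The row for subsequent therapy in Table 4.2.1-1 repeats the condition ("started without a prior reported progression per RECIST v1.1 criteria"), but the table is titled for PFS only and there is no DOR counterpart.

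Protocol 8.3.2 uses the same event definition and only the ordinary censoring. It has no separate rule for everyone who received later therapy; that sentence is an addition in the SAP. Section 5.1 of the protocol's RECIST appendix (Appendix 6) also ends response at the first documented progression. Protocol 8.4.2 states that DOR will be estimated by Kaplan-Meier.

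**The concern.** The third part of the bullet does not ask whether progression came before or after the new therapy. A responder with RECIST progression who then moves to another treatment satisfies the first part (event) and the third part (censored) together, and nothing in the bullet says which prevails.

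This is an expected sequence. Protocol 3.1 states "Subjects in the survival follow-up period who progress will be eligible to receive anti-cancer therapy as appropriate", and the footnotes to the on-treatment and follow-up schedule have the start dates of new therapies recorded. Protocol 3.4.2 allows palliative local therapy only in subjects considered to have progressed, and the footnote to Table 4.2.1-1 counts such therapy as subsequent anticancer therapy.

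Response duration is named in the first secondary objective. Two programmers who each follow the text faithfully could report different medians from the same data, and the literal version errs in the drug's favor.

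**Working it through.** **1. The rules side by side**

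| Source | Progression, then new therapy | New therapy without progression |
|---|---|---|
| SAP 4.2.1, DOR definition | Event | Not addressed |
| SAP 4.2.1, DOR later-therapy sentence | Censored | Censored |
| SAP 4.2.1 text and Table 4.2.1-1, PFS | Event | Censored |
| Protocol 8.3.2, DoR | Event | Not addressed |
| Protocol Appendix 6, section 5.1 | Ends at progression | Not addressed |

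Only the DOR later-therapy sentence turns a documented progression into a censored time. No other place in the available SAP text supplies the missing condition.

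**2. One subject.** Suppose a responder has RECIST progression on day 200 and starts a new drug on day 220. Under the definition, this is an event on day 200. Under the literal sentence, the subject is censored at the last scan before day 220. That is the day-200 scan, or a later one if another was done.

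**3. Direction.** Each Kaplan-Meier factor is 1 − d/r, with d events among r at risk. Recoding an event as censored on the same date lowers d and leaves r unchanged. Moving the subject to a later scan can only increase r in between. Either way the factors are no smaller and the curve is no lower, so the bias is upward.

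**4. The plan's own figures.** The documents give no DOR median, event count or precision, so there is no DOR figure to reproduce. SAP 5 does illustrate 10 or 13 responders among 50. Exact Clopper-Pearson 90% limits are 11.3% to 31.6% for 10/50 and 16.1% to 38.1% for 13/50, which match the stated (11%, 32%) and (16%, 38%). Those responder counts are used in step 6.

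**5. Size, closed form.** Assumptions: exponential DOR with a true median of 26 weeks, and a share q of all DOR events recoded as censored on the same date. The apparent hazard is (1 − q) times the true hazard, so:

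- apparent median = 26/(1 − q)
- apparent 26-week rate = 0.5^(1 − q)

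If a fraction of DOR events are deaths without progression, later therapy cannot recode them. With 30% such deaths (also an assumption), a share p of progressions recoded gives q = 0.7p.

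| Share of progressions recoded (p) | All events are progressions: median | 26-week rate | 30% deaths without progression: q | Median |
|---|---|---|---|---|
| 0 | 26 weeks | 50% | 0 | 26 weeks |
| 0.4 | 26/0.6 = 43 weeks | 66% | 0.28 | 26/0.72 = 36 weeks |
| 0.6 | 26/0.4 = 65 weeks | 76% | 0.42 | 26/0.58 = 45 weeks |

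**6. Size at the plan's responder counts.** This is a Kaplan-Meier simulation with an assumed true median of 6 months, 18 months of follow-up and 4,000 trials per setting. Entries are the typical (median) estimate across trials and, in brackets, the share of trials with the median not reached.

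| Responders | Progression counted as event | q = 0.3 | q = 0.5 | q = 0.7 |
|---|---|---|---|---|
| 10 | about 5.2 months (0.1%) | 8.2 (5%) | 12.0 (26%) | not reached (58%) |
| 13 | about 6.0 months (0.1% or less) | 8.6 (5%) | 12.0 (23%) | not reached (61%) |

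**The case against.** The best defense is that the sentence should not be read alone. The bullet opens by making progression an event, and censoring rules normally apply to subjects with no earlier event. The definition covers responders who progressed, and the ordinary rule covers those with neither progression nor new therapy. The remaining gap is new therapy without progression, which is plausibly what the added sentence was meant to fill. The PFS rule, Protocol 8.3.2 and the RECIST appendix all point the same way, so this is probably a drafting omission. That argument stands as to intent. It does not remove the contradiction, because the sentence as written covers all recipients of later therapy.

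Three stronger readings are tempting, and the documents do not support them.

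- **That most DOR events would be lost.** This needs q above 0.5, and no share is given. Some events will be deaths without progression. Routine status contacts run only to 6 months after last dose, and combination subjects may stay on study drug beyond progression (Protocol 4.5.7); both bear on how often later therapy is recorded.
- **That the median could be inflated fivefold.** That needs 80% of all events recoded, giving 26/0.2 = 130 weeks. Planned observation is about 51 weeks of treatment plus 6 months, or about 104 weeks with the nine-cycle extension. Retreatment or optional later scans could lengthen this, but a 130-week median would largely be a model extrapolation.
- **That Part 2 subjects who take the nivolumab extension would be censored at progression.** Protocol 3.1.2.1 keeps them in the main analysis through disease progression, and the SAP does not say that the extension counts as subsequent therapy.

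It is also fair that DOR drives no sample size or adaptation, that Protocol 8.5 plans no formal hypothesis testing, and that individual DOR and PFS are listed, so a mismatch could be noticed.

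**Conclusion.** The DOR censoring sentence is wrong as written. It conflicts with the definition in its own bullet, with the parallel PFS rule, with the protocol and with the RECIST appendix. If it is programmed literally, responders who progress and then start new therapy are censored on or after the progression scan, and DOR is biased upward.

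The direction is certain whenever at least one event is recoded; the size is not known. The figures of about 43 and 65 weeks for a 26-week true median assume exponential DOR and q of 0.4 and 0.6. With 30% of events as deaths without progression, the same shares of progressions recoded give about 36 and 45 weeks. The true median, the shares and the death fraction are all assumptions. A reader should not infer that the reported DOR will be overstated: a programmer who follows the definition or the PFS rule would avoid the error. Because DOR is a descriptive secondary endpoint, the effect is on the estimate and its confidence interval, not on type I error or any design decision.

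**What to change.** In SAP 4.2.1, restrict the later-therapy sentence for DOR to subjects with no prior reported progression per RECIST v1.1. Suggested wording: *Responders who start subsequent anticancer therapy before any RECIST v1.1 progression has been reported are censored at their last tumor assessment on or before the start of that therapy; progression or death before that start is an event.* Alternatively, extend Table 4.2.1-1 and its footnotes to DOR.

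The phrase *on or before* follows the table; the PFS text says only before. This is a separate, minor alignment worth making at the same time. It would also help to state whether the Part 2 combination extension counts as subsequent therapy, consistent with Protocol 3.1.2.1.

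The cost is one clause in the SAP before DOR is programmed. No new data are needed, since progression dates and therapy start dates are already collected.

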4.2.2 Pharmacokinetic Endpoints

The PK of the total antibody [unconjugated antibody + antibody conjugated to tubulysin or antibody conjugated to any tubulysin metabolites], active ADC [antibody conjugated to tubulysin], and unconjugated tubulysin of BMS-986183 (as monotherapy and in combination with nivolumab) will be characterized using the following endpoints:

- Cmax: Maximum observed serum concentration
- Tmax: Time of maximum observed serum concentration
- AUC(0-T): Area under the concentration vs time curve from 0 to time of the last measurable concentration
- AUC(TAU): Area under the concentration vs time curve in 1 dosing interval
- Ctau: Concentration at the end of a dosing interval
- Ctrough: Trough observed serum and/or plasma concentration, including predose concentrations and Ctau concentrations
- CLT: Total body clearance calculated as dose divided by AUC(TAU)
- Vss: Apparent volume of distribution at steady state
- Vz: Volume of distribution of terminal phase
- AI_Cmax: Accumulation index; ratio of Cmax at steady-state to Cmax after the first dose
- AI_Ctau: Accumulation index; ratio of Ctau at steady-state to Ctau after the first dose

- AI_AUCtau: Accumulation index; ratio of AUCtau at steady-state to AUCtau after the first dose
- Css-avg: Average concentration over a dosing interval calculated by dividing AUC(TAU) at steady state by tau
- T-HALF: Terminal serum half-life

4.2.3 ECG Endpoints

The effect of dosing regimen and exposure [active ADC and unconjugated tubulysin] of BMS-986183 as monotherapy on the QT interval will be measured by the following secondary endpoints:

- Changes in QTcF (Δ QTcF) from baseline, at selected times

4.2.4 Immunogenicity Endpoints

The immunogenicity of BMS-986183 (as monotherapy and in combination with nivolumab) will be measured by assessment of the presence or absence of specific ADA to BMS-986183. The incidence of positive ADA will be calculated.

Validated ADA test methods enable characterization of samples into ADA-positive vs ADA-negative. To classify the ADA status of a participant using data from an in vitro test method, each sample from a participant is categorized based on the following definitions:

Table 4.2.4- 1: Sample ADA Status

Sample ADA Status	Definition
Baseline ADA-positive sample	ADA is detected in the last sample before initiation of treatment
Baseline ADA-negative sample	ADA is not detected in the last sample before initiation of treatment
ADA-positive sample	1) an ADA detected (positive seroconversion) sample in a participant for whom ADA is not detected at baseline, or (2) an ADA detected sample with ADA titer to be at least 4-fold or greater (\geq) than baseline positive titer
ADA-negative sample	After initiation of treatment, ADA not positive sample relative to baseline

Next, using the sample ADA status, participant ADA status is defined as follows:

Table 4.2.4- 2: Participant ADA Status

ADA Status	Definition
Baseline ADA-positive	A participant with baseline ADA-positive sample
ADA-positive	A participant with at least one ADA positive-sample relative to baseline at any time after initiation of treatment
• Persistent Positive (PP)	ADA-positive sample at 2 or more consecutive timepoints, where the first and last ADA-positive samples are at least 16 ^c weeks apart
• Not PP-Last Sample Positive	Not persistent positive with ADA-positive sample at the last

ADA Status	Definition
	sampling timepoint
• Other Positive	Not persistent positive with ADA- negative sample at the last sampling timepoint
Neutralizing Positive:	At least one ADA-positive sample with neutralizing antibodies detected.
ADA-negative	A participant with no ADA-positive sample after the initiation of treatment

^c 16 week threshold was chosen based on the planned ADA blood sampling every four cycles of study therapy.

